14.3. Efficacy Analysis

Descriptive statistics (mean, median, standard deviation, minimum, and maximum) for continuous data and number (n) and percentage (%) for categorical data will be presented for all efficacy and safety parameters.

All efficacy assessments will be summarized by randomized treatment group.

14.3.1. Primary Efficacy Analyses

Null Hypothesis:

The null-hypothesis to be tested is that there is no difference in effect between the active treatment group and placebo in the change from Baseline to Week 12 in the ABC-C_{FXS} Social Avoidance subscale.

The change from Baseline in the ABC-C_{FXS} Social Avoidance subscale will be analyzed using MMRM. The MMRM will contain fixed effects for treatment, visit, study site, region and treatment-by-visit interaction as factors as well as the continuous fixed covariate of Baseline value for the dependent variable of interest. For the MMRM model, descriptive statistics will be presented by visit, which will include least-squares mean, least-squares standard errors of the mean, least-squares mean treatment difference (active-placebo), 95% confidence intervals around the least-squares (LS) mean treatment difference and p-values for between treatment group tests. MMRM will model the data specifying an unstructured variance-covariance structure. Details will be presented in the SAP for situations where convergence is not met using the unstructured variance-covariance structure.

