2. SYNOPSIS

Name of Sponsor/Company: Zynerva Pharmaceuticals Pty., Ltd. Zynerva Pharmaceuticals, Inc.
Name of Investigational Product (IP): ZYN002
Name of Active Ingredient: Cannabidiol (CBD)
Title of Study: A Randomized, Double-Blind, Placebo-Controlled, Multiple-Center, Efficacy and Safety Study of ZYN002 Administered as a Transdermal Gel to Children and Adolescents with Fragile X Syndrome - CONNECT-FX
Study Centers: Australia, Canada, New Zealand, and the United States of America
Study Period (years): Estimated date first patient enrolled: June 2018 Estimated date last patient enrolled: January 2020 Estimated date last patient completed: May 2020

Objectives:**Primary:**

To evaluate the efficacy of ZYN002 administered as a transdermal gel formulation, for up to 12 weeks, in patients ages 3 to < 18 years, in the treatment of symptoms of Fragile X Syndrome (FXS). The primary endpoint is the change from Baseline to Week 12 in the Aberrant Behavior Checklist-Community FXS Specific (ABC-C_{FXS}) Social Avoidance subscale.

Secondary:

To further evaluate the efficacy of ZYN002 in the treatment of symptoms of FXS.

To evaluate the safety of ZYN002 in the treatment of symptoms of FXS.

To evaluate CBD, CBD metabolite and tetrahydrocannabinol (THC) exposure.

Methodology:

This is a randomized, double-blind, placebo-controlled, multiple-center study, to assess the efficacy and safety of CBD administered as ZYN002, a transdermal gel, for the treatment of child and adolescent patients with FXS. Male and female patients with FXS will be treated for 12 weeks with a [REDACTED] single-blind placebo lead-in preceding the 12-week double-blind treatment period.

Approximately 204 male and female patients, ages 3 to < 18 years, will be randomized 1:1 to either trial drug or placebo. Randomization will be stratified by gender, weight category and region.

Site-specific supplemental protocols may be implemented in a subset of ZYN2-CL-016 patients.

Study Screening:

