The sample size was estimated for the primary efficacy endpoint using Power Analysis and Sample Size Software (PASS¹⁵) (NCSS, 2017). Sample size requirements were based on a previous Phase 1/2 trial, ZYN2-CL-009, in patients with FXS and on published results in the literature with other studied treatments in this indication. A sample size of 102 patients per treatment group (204 patients total) is required for the detection of a 1.3-point difference (assuming a standard deviation of 2.8) in the ABC-C_{FXS} Social Avoidance subscale score between treatments (active versus placebo) using a 2-sided test at the 5% significance level with 90% power.

Descriptive statistics (mean, median, standard deviation, minimum, and maximum) for continuous data and number (n) and percentage (%) for categorical data will be presented for all efficacy and safety parameters.

All efficacy assessments will be summarized by randomized treatment group.

Unless otherwise stated, mixed effects models for repeated measures (MMRM) will contain fixed effects for treatment, visit, study site, region and treatment-by-visit interaction as factors as well as the continuous fixed covariate of baseline value for the dependent variable of interest.

Analysis of covariance (ANCOVA) models will contain fixed effects for treatment and study site and region with baseline value for the dependent variable of interest as a covariate.

For MMRM/ANCOVA, descriptive statistics will be presented by visit, which will include least-squares mean, least-squares standard errors, and p-values for between treatment group tests.

The statistical comparison of active versus placebo for the primary endpoint of change from baseline in ABC-C_{FXS} Social Avoidance scores will be based on MMRM. The same model used for the primary endpoint analysis will also be used for the key secondary endpoints of change from Baseline in ABC-C_{FXS} Irritability, and Socially Unresponsive/Lethargic subscale scores. The statistical comparison of active versus placebo for the key secondary endpoint of CGI-I will be based on Wilcoxon rank sum test.

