7. INVESTIGATIONAL PLAN

7.1. Overall Study Design

This is a randomized, double-blind, placebo-controlled, multiple-center study, to assess the efficacy and safety of CBD administered as ZYN002, a transdermal gel, for the treatment of child and adolescent patients with FXS. Male and female patients with FXS will be treated for 12 weeks with a [REDACTED] single-blind placebo lead-in preceding the 12-week double-blind treatment period. Approximately 204 male and female patients, ages 3 to < 18 years, will be randomized 1:1 to either trial drug or placebo to attain a sample size of 102 subjects in each treatment arm. Randomization will be stratified by gender, weight category and region.

Figure 2: Study Design

*After completing 12 weeks of treatment, the patient has the option to move into the Open Label Extension (OLE) Study. If not moving into the OLE Study, the patient will complete the study unless they are on AEDs. If a patient is on AEDs, they will taper then move to the EOS visit.

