11.4. Method of Treatment Assignment or Randomization

Patients will be randomly assigned to treatment according to a computer generated randomization scheme. Randomization will be coordinated centrally through an interactive response system (IRT). The system will provide patient identification numbers at Screening, which are subsequently linked to the treatment assignments at randomization. Following completion of all evaluations at Visit 3, patients who meet all eligibility requirements and randomization criteria will be randomly allocated to active or placebo treatment groups using a 1:1 allocation ratio. Randomization will be stratified by gender (Male vs. Female), weight (≤ 35 kg vs. > 35 kg) and region (North America vs. non-North America).

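### Minor: the primary MMRM and the ANCOVA leave out gender and weight category, two of the three factors that stratify randomization

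*Combined protocol and SAP*

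**What the plan says.** **Randomization.** Section 7.1 states: "Randomization will be stratified by gender, weight category and region". Section 11.4 gives the levels: "Randomization will be stratified by gender (Male vs. Female), weight" (split at 35 kg) and "region (North America vs. non-North America". The Synopsis repeats the three factors.

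**Primary model.** Section 14.3.1: "The MMRM will contain fixed effects for treatment, visit, study site, region and treatment-by-visit interaction as factors", with the baseline value of the outcome as a continuous covariate and an unstructured covariance matrix. The only detail that this section hands to the SAP is what to do if that matrix does not converge. The Synopsis lists the same terms: "mixed effects models for repeated measures (MMRM) will contain fixed effects for treatment, visit, study site, region and treatment-by-visit interaction as factors". The ABC-C_FXS key secondary endpoints (Section 14.3.2) and the ABC-C_FXS and ADAMS secondary endpoints (Section 14.3.3) use the same model.

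**ANCOVA.** Synopsis: "Analysis of covariance (ANCOVA) models will contain fixed effects for treatment and study site and region with baseline value". Section 14.3.3 agrees and applies it to the Family Impact PedsQL.

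No visible text adds gender or weight category to either model, explains their absence, or plans a sensitivity analysis that includes them. Section 14 promises further methodology in an SAP that was not supplied, so what that SAP says on this point is unknown.

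**The concern.** Stratification makes the arms more alike on the stratifying factors, so the true sampling variance of the treatment difference falls if those factors are prognostic. A model that omits them leaves their variance in the residual and reports a standard error that is too large. Confidence intervals are then too wide, the test runs below its nominal 5%, and some power is given away.

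The choice of which factor to keep is also odd. Region is fixed by site: the centers are in four countries ("Study Centers: Australia, Canada, New Zealand, and the United States of America") and region is only North America or not. Once site is a fixed effect, region adds nothing to the treatment contrast. The model therefore keeps the one stratification factor that cannot help and leaves out the two that might. Weight category is also a design factor in its own right, because Section 7.4 ties the dose level to it.

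What is at stake is precision, not validity. The direction of any error is conservative.

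**Working it through.** **Inputs from the documents (Synopsis, Statistical Methods).** "detection of a 1.3-point difference (assuming a standard deviation of 2.8", 102 per arm, two-sided 5%, 90% power.

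**Reproducing the plan's figure.** SE = 2.8 × sqrt(2/102) = 0.392, so z = 1.3/0.392 = 3.316 and power = Φ(3.316 − 1.960) = 91.2% (91.0% by noncentral t). For 90% power the requirement is 98 per arm by normal approximation and 99 by noncentral t. The stated 102 is consistent with its inputs.

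**Effect of the omission.** Let R² be the share of residual variance, after baseline and site, that gender and weight category explain together. The documents give no value; 2%, 5% and 10% are illustrations, not bounds. With stratified 1:1 allocation:

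- SE overstated by the factor 1/sqrt(1 − R²)
- true alpha with factors omitted = 2 × [1 − Φ(1.960/sqrt(1 − R²))]
- power omitted = Φ((3.316 − 1.960)/sqrt(1 − R²))
- power included = Φ(3.316/sqrt(1 − R²) − 1.960)

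| R² | SE overstated | Alpha omitted | Power omitted | Power included | Gain (points) |
|---|---|---|---|---|---|
| 0 | 0% | 5.0% | 91.2% | 91.2% | 0 |
| 2% | 1.0% | 4.8% | 91.5% | 91.8% | 0.3 |
| 5% | 2.6% | 4.4% | 91.8% | 92.5% | 0.7 |
| 10% | 5.4% | 3.9% | 92.4% | 93.8% | 1.4 |

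**What gaps those R² values imply.** For a binary factor with share p and adjusted gap g in change, R² = p(1 − p)g²/2.8². Section 7.2 caps females at 25% of those screened, so the randomized share is unknown. I assume 10% to 25% female and weight splits from 30/70 to 50/50.

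- g = 0.65 for each factor: smallest total (0.09 + 0.21) × 0.4225/7.84 = 1.6%; largest (0.1875 + 0.25) × 0.4225/7.84 = 2.4%. The table's formulas give a gain of 0.25 to 0.36 points.
- g = 1.3 for each: gender 1.9% to 4.0%, weight 4.5% to 5.4%, total 6.5% to 9.4%; gain 0.95 to 1.34 points.

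**Simulation with the structure of the primary model.** All of these inputs are assumed: 204 patients, three visits, REML with unstructured covariance, visit SD 2.8, between-visit correlation 0.6, 10% monotone random dropout, blocks of 4 within strata, 70% of sites in North America, no site variance, factor effects constant over visits, R² split equally between the two factors, and 10,000 to 15,000 trials per cell.

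| Sites, % female | Gain at R² = 0 | 2% | 5% | 10% |
|---|---|---|---|---|
| 10, 15% | 0.04 | 0.35 | 0.93 | 1.94 |
| 20, 15% | −0.03 | 0.44 | 1.06 | 2.12 |
| 20, 25% | −0.01 | 0.30 | 0.88 | 1.89 |
| 30, 15% | −0.13 | 0.44 | 1.39 | 2.56 |

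Gains are in percentage points of power, with Monte Carlo SE 0.04 to 0.13. With 20 sites and 15% female, power without/with the factors is 86.9/86.8% at R² = 0 and 88.1/90.2% at 10%. Absolute power sits below the table above because of the assumed dropout and the site terms, so only the differences should be read. At R² = 10%, across the four cells, alpha is 3.7% to 4.3% omitted and 4.6% to 5.2% included (Monte Carlo SE about 0.2). A separate, simpler simulation (one visit, 4,000 trials per setting, 25% female) gives at R² = 10% a null rejection rate of 3.7% omitted against 4.8% included, and power of 92.3% against 93.9%.

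**Region and site.** With site and region both entered as crossed fixed effects, the region column is a sum of site columns. The treatment difference, its SE and its p-value do not change. The by-arm LS means are not estimable when the regions have unequal numbers of sites, and become estimable when site is nested in region.

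**The case against.** The strongest reply is that no harm is shown. The documents do not establish that gender or weight category predicts change. Section 5.1 says males typically have more severe symptoms, but that concerns level, which the baseline covariate covers at least in part. Power at the design assumptions exceeds 90% without the extra terms. All of this stands, and it is why the point is minor.

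The larger gains also need strong effects. With R² split equally, the 10% row requires a gender gap in change of sqrt(0.05 × 2.8²/(0.15 × 0.85)) = 1.75 points at 15% female, or 1.45 points at 25%, both above the 1.3-point treatment effect. Even the 5% row needs 1.24 points at 15% female. So the modest-gap figure of about 0.25 to 0.36 points is the more realistic guide. The simulated gains are larger partly because the assumed dropout lowers the starting power.

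Weight sets the number of sachets in both arms, so a dose difference would appear as a treatment-by-weight interaction, which a weight main effect does not model. That is correct: the case for the weight term rests on its role in randomization and its possible prognostic value.

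Finally, the Synopsis model sentence allows for stated exceptions, and the unseen SAP could add the terms. It could, but Section 14.3.1 lists the terms without that reservation and names only non-convergence for later detail. None of these replies gives a reason to leave the factors out.

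**Conclusion.** The concern holds as a minor point. The analysis does not follow the randomization for gender and weight category, and the one stratification factor it keeps is already determined by site. The consequence, if there is one, is an overstated standard error: 1.0% at an assumed R² of 2% and 5.4% at 10%. The matching loss of power is 0.3 to 1.4 points by normal approximation and 0.3 to 2.6 points in the simulation. If neither factor is prognostic, nothing is lost. R², the female share, the weight split, the number of sites and dropout are all assumptions. The conclusion that the omission is conservative and unbiased does not depend on their values.

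**What to change.** Before unblinding, add gender and weight category as fixed effects to the MMRM (Synopsis and Section 14.3.1) and the ANCOVA (Synopsis and Section 14.3.3), and carry the same terms into the SAP. If the sponsor prefers to leave them out, the SAP should give the reason, though that alone would not recover the precision. In the same edit, drop region or declare site nested within region, so that the by-arm LS means are estimable.

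The cost is two degrees of freedom and a few words; both factors are already recorded for randomization. If neither is prognostic, the simulated loss of power is at most 0.13 points. Section 19 already carries COVID-19 modifications, so this would be a late change to the primary model. It must be dated and documented as made before unblinding.

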14.3.2. Key Secondary Efficacy Analyses

The key secondary endpoint, change from Baseline to Week 12 in the ABC-C_{FXS} Irritability, and ABC-C_{FXS} Socially Unresponsive/Lethargic subscale score, will be analyzed using the same MMRM approach as the primary endpoint.

The CGI-I at Week 12/ET will be analyzed using the Wilcoxon rank sum test.

The response rate for the percent of patients who have $\geq 25\%$ improvement at Week 12/ET from Baseline in the ABC-C_{FXS} Irritability, and ABC-C_{FXS} Social Avoidance subscale score will be compared using the chi-square test and binomial confidence intervals.

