7.2. Number of Patients

Approximately 204 male and female patients will be randomized 1:1 to either trial drug or placebo. No more than 25% of the patients screened will be females.

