7.6.19.4. Clinical Global Impressions Scale-Severity and Improvement

The Clinical Global Impression Scales, Severity (CGI-S) and Improvement (CGI-I), are commonly used in clinical trials (Leigh et al. 2013) as they allow the clinician to utilize the history from the caregiver and incorporate the score into a clinical rating for the severity of symptoms. CGI-S will be assessed at Screening, Visit 2, Visit 3, Visit 4, Visit 5, and Visit 6/ET to judge the severity of the symptoms of FXS at the onset of and throughout the study. CGI-I will be assessed at Visit 3, Visit 4, Visit 5, and Visit 6/ET.

CGI-S is a 7-point scale that requires the clinician to rate the severity of the patient's illness at the time of assessment, relative to the clinician's past experience with patients who have the same diagnosis. Considering total clinical experience, a patient is assessed on severity of mental illness at the time of rating 1 - normal, not at all ill; 2 - borderline mentally ill; 3 - mildly ill; 4 - moderately ill; 5 - markedly ill; 6 - severely ill; or 7 - extremely ill.

CGI-I is a 7-point scale that requires the clinician to assess how much the patient's illness has improved or worsened relative to a Baseline state at the beginning of the intervention and rated as: 1 - very much improved; 2 - much improved; 3 - minimally improved; 4 - no change; 5 - minimally worse; 6 - much worse; or 7 - very much worse. Information from both the clinician and the parent/caregiver history are incorporated into a clinical rating.

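### The CGI-I and responder tests ignore the randomisation strata: they are valid as planned, but stratified versions would keep some power if the strata prove prognostic

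*Combined protocol and SAP*

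**What the plan says.** - **Randomisation (Section 11.4).** "Randomization will be stratified by gender (Male vs. Female), weight" (up to 35 kg or above) and region (inside or outside North America). That makes 2 x 2 x 2 = 8 cells, with 1:1 allocation.
- **CGI-I, a key secondary endpoint (Section 11.2).** Section 14.3.2: "The CGI-I at Week 12/ET will be analyzed using the Wilcoxon rank sum test". The Synopsis agrees: "The statistical comparison of active versus placebo for the key secondary endpoint of CGI-I will be based on Wilcoxon rank sum test". Section 14.3.3 names the same test for Weeks 4 and 8. None of these places names a stratification factor.
- **Responder endpoints.** For the 25% improvement rates on Social Avoidance and Irritability, Section 14.3.2 says they "will be compared using the chi-square test and binomial confidence intervals". Section 14.3.3 uses the same method for CGI-I improved and for the combined responder definition. Section 11.3 lists all of these as ordinary secondary endpoints.
- **Other analyses, for comparison.** Section 14.3.1: "The MMRM will contain fixed effects for treatment, visit, study site, region and treatment-by-visit interaction as factors", plus the baseline value. The ANCOVA in Section 14.3.3 also has region and site. Neither model has gender or weight. CGI-S gets a Cochran-Mantel-Haenszel (CMH) test adjusted for baseline score.
- **Deferred detail.** Section 14 leaves further analysis methodology to an SAP written after protocol approval. That SAP is not in the supplied text.

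**The concern.** Stratified randomisation balances the arms within each cell. If the cells differ in outcome, that balance makes the treatment comparison more precise. A test that ignores the cells still counts the between-cell spread as noise. It then overstates the variance of the comparison, so its true size falls below 5% and some available power is lost.

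CGI-I has no baseline value to adjust for, because it is rated "relative to a Baseline state at the beginning of the intervention". The randomisation factors are therefore the natural pre-specified adjusters, and this key secondary test uses none of them. At stake is a modest amount of power for CGI-I and the responder endpoints. The validity of the tests is not at stake.

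**Working it through.** **1. The plan's own figure.** The Synopsis sizes the trial at 102 per arm for a "1.3-point difference (assuming a standard deviation of 2.8"), two-sided 5%, 90% power, on Social Avoidance.

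- Normal approximation: n per arm = 2 x [(1.960 + 1.282) x 2.8 / 1.3]^2 = 97.5, so 98.
- A noncentral t calculation gives 99 per arm, and 91.0% power at 102. The stated size is reproduced closely enough.
- Standardised effect: 1.3 / 2.8 = 0.464 SD.

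The documents give no effect size or power for CGI-I or any responder endpoint, so the rest is scenario work.

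**2. Assumptions.** Only 204, 1:1, the three factors and 0.464 SD come from the documents, and applying 0.464 SD to CGI-I is itself an assumption. Also assumed:

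- 75% male, 55% at or below 35 kg, 70% in North America;
- permuted blocks of 4 within the 8 cells;
- an unconditional two-sided 5% test;
- the same treatment effect in every cell;
- placebo CGI-I cumulative shares of 8/30/55/85/95/99%;
- one binary endpoint, CGI-I improved, at 30% on placebo.

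**3. Variance due to strata.** Total SD is held at 1 (= 2.8 points). For an effect of d SD per factor:

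strata variance = d^2 x (0.75 x 0.25 + 0.55 x 0.45 + 0.70 x 0.30) = d^2 x (0.1875 + 0.2475 + 0.21) = 0.645 d^2

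This is 2.6% at d = 0.2, 5.8% at 0.3 and 16.1% at 0.5. Residual SD at 0.5 is sqrt(1 - 0.161) = 0.916.

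**4. Tests compared.**

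- Van Elteren: sum over cells of w_h x (rank sum minus its expectation), divided by the square root of the sum of w_h^2 x (tie-corrected variance), with w_h = 1/(N_h + 1). The Wilcoxon test is the one-cell case.
- CMH: sum over cells of (active responders minus n1_h m_h / N_h), divided by the square root of the sum of n1_h n0_h m_h (N_h - m_h) / [N_h^2 (N_h - 1)]. Pearson chi-square is the unstratified comparison. No continuity correction is used.

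**5. Results** (200,000 runs per scenario; Monte Carlo SE 0.07 to 0.10 points for power, about 0.05 for size; differences taken before rounding).

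| Effect per factor | Wilcoxon power | Van Elteren power | Diff. | Chi-square power | CMH power | Diff. | Wilcoxon size |
|---|---|---|---|---|---|---|---|
| 0 | 87.9% | 87.4% | -0.6 | 74.0% | 73.5% | -0.5 | 4.9% |
| 0.2 SD | 88.3% | 88.2% | -0.1 | 74.3% | 74.3% | 0.0 | 4.7% |
| 0.3 SD | 88.6% | 89.2% | +0.6 | 74.6% | 75.2% | +0.6 | 4.4% |
| 0.5 SD | 89.6% | 92.1% | +2.5 | 75.2% | 77.9% | +2.7 | 3.5% |

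Van Elteren size stays at 4.9 to 5.0% throughout.

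**6. Hand checks.**

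- Size at 0.5 SD: with perfect balance the unstratified statistic has true SD of about 0.916, so the 1.96 cut-off acts like 1.96 / 0.916 = 2.14, a two-sided tail of about 3.2%. The simulated 3.5% is close.
- Chi-square with no strata effect: the active rate is Phi(-0.524 + 0.464) = 47.6%. The null SE is sqrt(0.388 x 0.612 x 2/102) = 0.068 and the alternative SE is sqrt[(0.476 x 0.524 + 0.30 x 0.70)/102] = 0.067. Then (0.176 - 1.96 x 0.0682) / 0.0671 = 0.63, a power of about 74%.

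**7. One prognostic factor only, at 0.5 SD.** CGI-I: gender 88.4 v 88.7%, weight 88.7 v 89.3%, region 88.6 v 89.0%. Responders: 74.3 v 74.7%, 74.4 v 75.1%, 74.5 v 75.0%. The gain is 0.3 to 0.7 points.

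**8. Other shares.** With 50% above 35 kg, 35% outside North America and 25% improved on placebo (4,000 runs), CGI-I power moved from 87.5 to 87.2% with no strata effect, 89.0 to 89.0% at 5% of variance, 89.0 to 90.5% at 10% and 89.4 to 93.0% at 20%. The pattern is the same.

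**9. Cell sizes.** Section 7.2: "No more than 25% of the patients screened will be females". That is a ceiling, and it applies to screening, so the randomised share may be lower.

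| Female share | Smallest of 8 cells | Smallest of 6, pooling region within females |
|---|---|---|
| 25% | 204 x 0.25 x 0.45 x 0.30 = 6.9 | males above 35 kg, outside North America: 204 x 0.75 x 0.45 x 0.30 = 20.7 |
| 15% | 204 x 0.15 x 0.45 x 0.30 = 4.1 | females above 35 kg: 204 x 0.15 x 0.45 = 13.8 |

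At 25% female, the 6-cell tests keep the gain at 0.5 SD per factor (CGI-I 92.0%, responders 77.8%) and lose about 0.4 points with no strata effect. At 15% female, a smaller run (10,000) put the CGI-I gain at about +0.3 points for 0.3 SD and +2.0 for 0.5 SD.

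**The case against.** The strongest reply is that this is a preference and not an error. Wilcoxon and chi-square tests are valid after stratified randomisation. No part of the documents says that gender, weight or region predicts improvement, and rating each patient against their own baseline may remove much of any such relation. Stratifying can slightly hurt. The plan states adjustment where it wants it, as for CGI-S, so the omission may be deliberate, and the SAP may already name stratified tests. All of this stands, and it is why the point is optional and its range starts below zero.

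Several limits on the numbers also stand. Block size is not given. The text of the multiplicity section (14.7) is redacted, so the level and order at which CGI-I is tested are unknown. Daily dose differs by weight category (Section 9.1), so a constant effect across weight strata is a simplification. Only CGI-I improved was modelled; the 25% improvement and combined responder rates were not. Finally, a CMH test beside unstratified binomial intervals would leave test and interval mismatched, so the fix has to cover both.

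What the reply does not remove is that the factors were considered important enough to stratify on, that these tests ignore them, and that the SAP can settle the matter at almost no cost.

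**Conclusion.** The point holds as a low-priority efficiency improvement. The planned CGI-I and responder tests are valid. They become conservative if the strata are prognostic: CGI-I size is about 3.5% at 0.5 SD per factor. Stratifying is worth between about -0.6 and +2.7 points of power over the scenarios from no effect to 0.5 SD on all three factors, and close to nothing at 0.2 SD per factor. The figures rest on the assumptions in step 2 of the working. Confidence is medium, because the strength of the strata is unknown.

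Three stronger readings are not supported:

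- **Inflated Type I error.** A reader might infer that ignoring the strata makes the tests anti-conservative. The error runs the other way.
- **Power below plan.** A reader might infer that prognostic strata reduce the power of the planned tests. With total SD held at the stated 2.8, Wilcoxon power rises slightly, from 87.9 to 89.6%. The tests miss part of an available gain.
- **An expected gain of 2.5 points or more.** In these scenarios that needs all three factors at 0.5 SD together, which the documents do not establish. One such factor alone gives 0.3 to 0.7 points.

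**What to change.** Before unblinding, specify in the SAP:

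1. CGI-I at Week 12/ET, and at Weeks 4 and 8: van Elteren test stratified by gender, weight category and region as randomised.
2. Responder endpoints: CMH test with the same strata, reported with a Mantel-Haenszel stratified risk difference and its 95% confidence interval. Binomial intervals for each arm can stay as description.
3. A pooling rule fixed in advance for sparse cells, for example pooling the two regions within females, which leaves 6 strata.
4. The unstratified Wilcoxon and chi-square tests as sensitivity analyses.

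If the SAP already says this, confirming it is enough.

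**Cost.** Wording and minor programming. No new data are needed, because the three factors are already recorded for randomisation. The statistical downside is about 0.5 to 0.6 points of power if the strata are not prognostic (about 0.4 with the 6-stratum rule), and the pooling rule has to be written and followed.
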